7.6 MAIN ANALYSES

Descriptive summaries of baseline patient characteristics as specified in [Section 5](#) will be created for the overall population and by anticoagulation treatment. These analyses will be repeated by the subgroup variables defined in [Section 6.4](#).

Descriptive summaries of anticoagulation treatment patterns, including the observed combinations of treatment at baseline and at hospital discharge/14 days as described in [Table](#)

[6.1: 1](#), will be created for the overall population. These analyses will be repeated by the subgroup variables defined in [Section 6.4](#).

As an exploratory analysis, baseline characteristics of the dabigatran patients will be summarized separately by the following dose groups, if the subgroups consist of at least 200 patients:

- 150 mg b.i.d.
- 110 mg b.i.d.
- 75 mg b.i.d.
- Other doses

7.8 EXPOSURE TIME

As no follow up is included and only the anticoagulation treatment at baseline is captured, exposure time will not be calculated.

7.9 SAFETY ANALYSIS

7.9.1 Adverse drug reactions

For Objective 1, patients will not be followed up after hospital discharge or 14 days after baseline. If the investigator becomes aware of an event at the baseline visit or when entering the data collected at the baseline visit that is deemed by the investigator to be related to a Boehringer Ingelheim drug, the investigator is responsible for entering this information in the Adverse Drug Reactions/Adverse Events with Fatal Outcome page of the eCRFs. However, these data will not be analyzed for Objective 1. A listing of all reported ADRs/fatal AEs will be provided in the study report appendix.

7.9.2 Laboratory data

All laboratory variables will be summarized descriptively. Creatinine clearance (mL/min) will be derived based on the collected serum creatinine data using the Cockcroft-Gault formula [\[3\]](#).

7.9.3 Vital signs

Weight, height, blood pressure (systolic and diastolic), heart rate and respiratory rate will be collected at baseline and summarized descriptively.

7.9.4 ECG

Electrocardiogram (ECG) assessments are not collected as part of this study.

7.9.5 Others

No other assessments or data collection are planned for Objective 1.

7.10 INTERIM ANALYSES

It is planned that one interim analysis will be performed for Objective 1 based on data from approximately the first 3,000 patients. The interim analysis will include all the relevant analyses described in this SEAP.

The final analysis will be performed once the data collection for all enrolled patients is completed, the data sets are cleaned and the database is locked for Objective 1.

2. LIST OF ABBREVIATIONS

Term	Definition / description
ACS	Acute coronary syndrome
AE	Adverse Event
ADR	Adverse Drug Reaction
BI	Boehringer Ingelheim
b.i.d.	Bis in die (two times a day)
BMI	Body Mass Index
DE	Dabigatran etexilate
DVT	Deep vein thrombosis
eCRF	Electronic Case Report Form
ePS	Estimated Propensity Score
ICH	International Conference on Harmonisation
IPD	Important protocol deviation
IPTW	Inverse probability of treatment weighting
ISPE	International Society for Pharmacoepidemiology
ISTH	International Society on Thrombosis and Haemostasis
ITT	Intention-to-treat
MedDRA	Medical Dictionary for Regulatory Activities
MI	Multiple Imputation
MQRM	Medical Quality Review Meeting
NCB	Net clinical benefit
NIS	Non-interventional study
PACT-Q2	Satisfaction with anticoagulation treatment
PD	Protocol deviation
PE	Pulmonary embolism
Q1	Lower quartile
Q3	Upper quartile
SD	Standard deviation
SEAP	Statistical and epidemiological analysis plan
STEMI	ST elevation myocardial infarction
TTR	Time in therapeutic range
UA	Unstable Angina

Term	Definition / description
ACS	Acute coronary syndrome
VKA	Vitamin K antagonist
VTE	Venous thromboembolism
WHO	World Health Organization

3. INTRODUCTION

As per ICH E9 [1] and the ISPE Guidelines of Good Pharmacoepidemiology Practice [2], the purpose of this document is to provide a more technical and detailed elaboration of the principal features of the analysis described in the protocol, and to include detailed procedures for executing the statistical analysis of the data. This document describes the final analysis at the end of study for Objective 2.

This SEAP assumes familiarity with the non-interventional study (NIS) protocol including Protocol Amendments. In particular, the SEAP is based on the planned analysis specification as written in the NIS protocol Section 9 “Research Methods”. Therefore, SEAP readers may consult the NIS protocol for more background information on the study, e.g., on study objectives, study design and population, treatments, definition of measurements and variables, planning of sample size.

SAS® Version 9.3 or higher will be used for all analyses.

4. CHANGES IN THE PLANNED ANALYSIS OF THE STUDY

None.

5. OUTCOMES

Objective 1 of the RE-COVER was described in a separate Document, “Statistical and Epidemiological Analysis Plan - Objective 1”.

The following two questions were investigated in the SEAP for Objective 1:

- With the approval of dabigatran etexilate and other non-vitamin K anticoagulants (NOACs), what treatments are being administered for acute VTE in routine clinical practice in the different regions of the world?
- When presenting with an acute VTE event, what factors influence the choice of treatment for the event?

Objective 2 of the RE-COVER study is designed to analyze the safety and effectiveness of dabigatran etexilate regimens in the treatment of DVT and PE over 1 year of follow-up in comparison to a VKA regimen.

Additional further exploratory objectives are:

- To evaluate geographical variations in health care resource utilization and patient satisfaction with their treatment in routine clinical practice.
- To conduct stratified analysis for the safety and effectiveness of dabigatran etexilate according to dose.

The following three questions will be investigated:

- What is the safety and effectiveness of dabigatran etexilate versus VKA under conditions of routine clinical practice?
- What health care resources are utilized in patients who are treated with dabigatran etexilate or VKA for an acute VTE under conditions of routine clinical practice?
- For patients who are treated with either dabigatran etexilate or VKA, what is patients’ satisfaction with their treatment under conditions of routine clinical practice?

5.1 MAIN OUTCOMES

The main outcomes for Objective 2 are:

- Primary safety outcome measure: ISTH Major bleeding and ISTH clinically relevant non major bleeding (CRNMB)
- Primary effectiveness outcome measure: symptomatic recurrent VTE including VTE-related mortality

A patient is considered to have major bleeding if the bleeding is fatal and/or meets at least one of the following criteria:

- Overt bleeding associated with a reduction in hemoglobin of at least 20 grams per liter or leading to a transfusion of at least 2 units of blood or packed cells

- Symptomatic bleeding in a critical area or organ: intraocular, intracranial, intraspinal, or intramuscular with compartmental syndrome, retroperitoneal bleeding, intraarticular bleeding or pericardial bleeding

A patient is considered to have clinically relevant non major bleeding if the bleeding caused at least one of the following actions:

- Leading to hospitalization or increased the level of health care
- Requiring medical intervention by a healthcare professional
- Prompting a face to face evaluation

5.2 SECONDARY OUTCOMES

The following secondary outcomes will be analysed from the time of diagnosis of the index event to 12 months post diagnosis:

- Recurrent DVT and/or PE
- VTE-related mortality
- All-cause mortality

6. GENERAL ANALYSIS DEFINITIONS

6.1 EXPOSURE

Patients will be analyzed in treatment groups (DE or VKA) according to the treatment that has been prescribed at the baseline visit and at hospital discharge or 14 days after the baseline visit and recorded in the Patient Status eCRF (obtained at enrolment). The start of the follow up will be defined as the initiation of each of these two treatments.

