### 9.3.2 Outcome measures

For [Objective 1](#):

The following primary outcome measures will be analyzed on data that is collected at the time of the acute VTE event:

- Demographic information (age and gender)
- VTE event information (event type and treatment for event)

The following further outcome measures will be analyzed on the collected baseline data:

- co-medication
- co-morbidities,

- basic physical examination data
- laboratory information
- VTE event information including location, extent and severity of the thrombus
- VTE risk factors
- history of VTE event
- bleeding risk

For [Objective 2](#):

The following primary outcomes will be analyzed from time of diagnosis of the index event to 12 months post diagnosis:

- Primary safety outcome measure: ISTH Major bleeding and ISTH clinically relevant non major bleeding (CRNMB)
- Primary effectiveness outcome measure: symptomatic recurrent VTE including VTE-related mortality

The following secondary outcomes will be analyzed from the time of diagnosis of the index event to 12 months post diagnosis:

- Recurrent DVT and/or PE
- VTE-related mortality
- All-cause mortality

The following further outcomes will be analyzed from time of diagnosis of the index event to 12 months post diagnosis:

- Life-threatening bleeding events
- Acute coronary syndrome (ACS)
- Serious adverse drug reactions
- Net clinical benefit (NCB)
- Satisfaction with anticoagulation treatment (PACT-Q2)
- Health care resource utilization

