6.3 PATIENT SETS ANALYSED

Three patient sets are defined: "all eligible", "all eligible treated", and "restricted"; the following rules are used to assess if a patient is included in an analysis set:

ALL ELIGIBLE: If a patient fulfills all inclusion criteria and no exclusion criteria.

ALL ELIGIBLE TREATED: If a patient fulfills all inclusion criteria and no exclusion criteria and took prescribed treatment at least once.

RESTRICTED: The restricted population is composed of all eligible patients within the trimmed patient set which lie within the region of propensity score overlap (for definition see Section 7). As the propensity score analysis will be based on eligible patients who at least once took the prescribed treatment, the restricted population excludes patients prescribed the treatment but who did not take it.

Number of patients included in the different patient sets will be shown by treatment group.

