6.7 BASELINE, TIME WINDOWS AND CALCULATED VISITS

The baseline analysis for Objective 2 is cross-sectional in nature. Patients will be assigned to the two treatment groups as described in Section 6.1. For the descriptive analysis, in addition to the data collected at the baseline visit, additional data at hospital discharge or 14 days after the baseline visit (whichever is later) will be collected and summarized descriptively. For the logistic regression analysis to produce estimated propensity scores, data up to the start of dabigatran or VKA treatment will be considered as baseline and will be used as model covariates.

Data from the longitudinal follow-up for collected laboratory data, healthcare resource utilization, and PACT-Q2 will be summarized descriptively at the time points given in [Table 5.3: 2](#). In case time windows will be needed in order to assign observations to visits, observations from 45 days to 134 days after diagnosis will be assigned to month 3, from 135 days to 269 days after diagnosis will be assigned to month 6 and more than 269 days will be assigned to year 1. In case more than one observation is assigned to a certain visit the observation closest to the calculated visit will be assigned. In case two or more observations are on the same day the last will be assigned. Month 3 corresponds to 91 days, month 6 to 182 days, and year 1 to 365 days.

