In the following if not stated otherwise for all analyses only patients from the restricted patient set are considered.

- 1.) Main analysis of the main outcomes (Major bleeding and clinically relevant non major bleeding, and symptomatic recurrent VTE including VTE-related mortality)

The main analysis will be a PS analysis using overlap weights. A Cox regression model including the overlap weights will be performed. In addition, the main outcomes will be analyzed within the subgroups defined in Section 6.4, when the number of patients per treatment group is at least 500. For the overlap weights analysis each patient in the treatment groups DE and VKA will be weighted proportional to the probability of that

patient being assigned to the opposite treatment group. The weights are called “overlap weights” and are calculated as follows:

$$\begin{aligned} O_{DE} &= 1 - P \\ O_{VKA} &= P \end{aligned}$$

where P is the estimated propensity score of a patient being assigned to the DE treatment group.

To assess baseline imbalance for the overlap weights by ePS, the mean of each covariate of interest will be calculated for patients in each of the treatment groups (DE and VKA). For binary variables, the proportion will be used instead. For categorical variables with more than two categories, dummy binary variables will be derived to represent each category and the proportion calculated for each of the treatments.

The standardized differences will be calculated for the mean for each covariate and the standardized differences (denoted as d) for the mean of a continuous variable is defined [10] as:

$$d = \frac{(\bar{x}_{DE} - \bar{x}_{VKA})}{\sqrt{\frac{s^2_{DE} + s^2_{VKA}}{2}}}$$

where \bar{x}_{DE} and \bar{x}_{VKA} denote the sample mean of the covariate in DE and VKA patients, respectively, while s^2_{DE} and s^2_{VKA} denote the sample variance of the covariate in DE and VKA patients, respectively.

For dichotomous variables, the standardized difference is defined as:

$$d = \frac{(\hat{p}_{DE} - \hat{p}_{VKA})}{\sqrt{\frac{\hat{p}_{DE} * (1 - \hat{p}_{DE}) + \hat{p}_{VKA} * (1 - \hat{p}_{VKA})}{2}}}$$

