3.) Analyses of secondary and further outcome events

The same Cox regression model as used for the primary outcomes will be used for the secondary and further outcomes, if enough events are reported. The ePS overlap weights analysis on the specific outcome event might be performed for all outcomes.

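### Objective 2 has no single time zero: the protocol counts outcomes from diagnosis, SAP 6.1 counts from treatment initiation, SAP 4 declares no change, and the visible text gives no entry time at consent

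*SAP*

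**What the plan says.** **Origin at diagnosis.** Protocol 9.3.2: "The following primary outcomes will be analyzed from time of diagnosis of the index event to 12 months post diagnosis". The same section gives the secondary outcomes the same window. SAP (Objective 2) 5.2 keeps it: "The following secondary outcomes will be analysed from the time of diagnosis of the index event to 12 months post diagnosis". SAP 5.1 lists the primary outcomes with no window.

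**Origin at treatment start.** SAP (Objective 2) 6.1, Exposure: "The start of the follow up will be defined as the initiation of each of these two treatments". Other parts of that SAP fit this origin. The treated set in 6.3 needs a patient who "took prescribed treatment at least once", 6.7 states that "data up to the start of dabigatran or VKA treatment will be considered as baseline" for the propensity model, and 7.8 measures exposure from first intake.

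**Model.** SAP 7.6, main outcomes: "A Cox regression model including the overlap weights will be performed". For the others: "The same Cox regression model as used for the primary outcomes will be used for the secondary and further outcomes", provided there are enough events.

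**Declared changes.** Under "4. CHANGES IN THE PLANNED ANALYSIS OF THE STUDY" the Objective 2 SAP enters only None.

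**Entry.** Protocol 9.1 and 9.2.1 allow Objective 2 enrolment up to 30 days after the VTE, and 9.2.4 requires a signed consent form. Protocol 9.2.4 and 9.9 ask sites not to leave out patients with early outcome events.

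**The concern.** Two things are at stake.

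First, someone programming the analysis can take either origin from the text. The end of follow-up is equally open: the only stated end, 12 months, is counted from diagnosis. Neither origin is neutral. A diagnosis clock applied to patients who must have taken the drug (SAP 6.3, 7.6) counts the days from diagnosis to first intake as time at risk, although no death can be observed in them. An initiation clock removes that problem but drops events before first intake from the analysis.

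Second, the initiation clock starts before some patients enter the study. A patient who dies after first intake but before consent is generally not enrolled, while those who survive to consent contribute that time. The rate formula, the weighted Cox model and the sensitivity analyses in SAP 7.6 state no entry time. Site training can preserve early non-fatal events but not early deaths. All-cause mortality is the most exposed outcome, because every event is fatal.

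**Working it through.** **1. The plan's own figure.** Protocol 9.5 uses HR 0.69, one-sided alpha 0.025, 90% power and the Freedman formula. Events = (1.960 + 1.282)² × (1.69/0.31)² = 10.507 × 29.72 = 312. With a VKA rate of 7.7% and 15% loss spread exponentially over the year, the mean event probability is 0.0604, so N is about 5,170 at HR 0.69. N is exactly 5,000 at HR 0.6853, which rounds to 0.69. The stated size is therefore reproduced, and the clock does not enter the formula. The 7.7% comes from an oral treatment period, which matches the initiation origin.

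**2. Length of the gap.** Protocol 9.2.4 gives 5 to 10 days of parenteral treatment before dabigatran: 5/365 = 1.4% and 10/365 = 2.7% of a year. At a constant hazard of −ln(1 − 0.077) = 0.080 per year, 2,500 × (1 − exp(−0.080 × d/365)) gives about 3 events for d = 5 and 5 for d = 10.

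**3. Effect of the choice of clock.** Assumptions: all first intakes are uniform over days 5 to 10 in both arms, HR is 1 before first intake and 0.69 after, pre-intake events are captured, and follow-up is 12 months. A share s of first-year VKA events falls evenly in days 0 to 7 and the rest evenly to day 365. The share before first intake is q = s × 6.6/7 + (1 − s) × 0.9/358; with a flat hazard it is 7.5/365. On the diagnosis clock, HR ≈ q + 0.69(1 − q).

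| Early events | q | HR, diagnosis clock | HR, initiation clock |
|---|---|---|---|
| flat | 2.1% | 0.70 | 0.69 |
| s = 5% | 5.0% | 0.71 | 0.69 |
| s = 10% | 9.7% | 0.72 | 0.69 |
| s = 20% | 19.1% | 0.75 | 0.69 |

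**4. Deaths before consent.** Assumptions: all-cause death, true HR 1, initiation-to-consent lag 14 days in VKA and 7 in DE. Let u be the share of first-year deaths that falls evenly in the first 30 days after initiation. Observed HR ≈ (1 − u × 7/30)/(1 − u × 14/30).

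- u = 8% (flat, 30/365): 0.981/0.962 = 1.02
- u = 20%: 0.953/0.907 = 1.05
- u = 30%: 0.930/0.860 = 1.08

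The reverse lags give the reciprocals. Equal lags give 1.00. If only 20% of an outcome's events are fatal, u = 30% gives (1 − 0.2 × 0.07)/(1 − 0.2 × 0.14) = 0.986/0.972 = 1.014.

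A simulation with a binary confounder and overlap weights as in SAP 7.6 (1.2 million patients, four replicates, standard error at most 0.012) gave 1.03, 1.05 and 1.09. With delayed entry at consent it gave 0.99 to 1.01, and with equal lags it also gave 0.99 to 1.01.

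**5. Price of a delayed-entry run.** With a flat hazard, 12 months of follow-up and a lag of 4 to 9 days, 312 × (1 − 4/365) = 309 and 312 × (1 − 9/365) = 304 events remain (power 90% and 89%). In an extreme case, with a 25-day lag and 30% of events in the first 30 days, 312 × (1 − 0.30 × 25/30) = 234 remain (power 80%).

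**The case against.** The strongest reply is that the SAP merely elaborates the protocol's own as-treated design. Protocol 9.7.2.1 makes the primary comparison as treated, 9.3.3 assesses exposure from the treatment start date, 9.5 takes its event rate from an oral treatment period, and 9.7.2.3 does not count adverse drug reactions before first intake. SAP 6.1 stands among the general definitions and is not limited to the primary outcomes. On this view SAP 5.2 simply repeats protocol wording. This stands as a defence of initiation as the origin. It does not remove the conflict with protocol 9.3.2 and SAP 5.2, nor the entry None in Section 4.

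A reader might infer that recurrent VTE runs on a different clock from the composite that contains it, and so could show more events. The documents do not establish that: the same Cox model is reused, and 6.1 can be read as covering every outcome. The secondary outcome of recurrent DVT and/or PE is also not restricted to symptomatic events, so it could exceed the primary count even on one clock.

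A reader might also infer that bias from time before consent is built in. It is not. Outcome events are collected at baseline (protocol Table 9.3.1:2), early events are no reason for exclusion, and enrolment of the two groups is meant to occur at similar time points (9.1). That leaves deaths, and only an arm difference in lag distorts the hazard ratio. No passage reports one.

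For switched patients, SAP 6.1 and 7.8 largely settle time zero as the first intake of DE or VKA. Patients already on one of these drugs for a previous VTE, whom protocol 9.2.2 does not exclude, remain unclear.

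**Conclusion.** The contradiction is certain and needs no assumption: protocol 9.3.2 and SAP 5.2 say diagnosis, SAP 6.1 says initiation, SAP 5.1 is silent, and no change is declared. Treatment initiation is the sounder origin here; the fault is that it is neither applied throughout nor declared. On the assumptions in step 3, the choice moves a hazard ratio of 0.69 to 0.70 with a flat hazard, and to 0.75 if a fifth of first-year VKA events fall in the first week.

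The entry-time point holds with moderate confidence. Under assumed lags of 14 and 7 days, the all-cause mortality hazard ratio shifts by about 2 to 8% over 12 months, in either direction, and not at all with equal lags. The documents give neither lags nor early-death shares. Larger shifts can be produced by assuming that as-treated censoring shortens follow-up for everyone, down to the three-month minimum planned duration. The documents do not support that as the expected case, and it still needs unequal lags. The comparison is exploratory (protocol 9.7.1), which limits the consequence.

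SAP 5.3, 6.4 and 7.7 and protocol 9.7.2.2 are not in the public text, so the absence of an entry rule is a statement about the visible text only.

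**What to change.** 1. State treatment initiation as the single time zero, with one end of follow-up, for all Objective 2 time-to-event outcomes.
2. Align SAP 5.2, add the window to 5.1, and record the difference from protocol 9.3.2 in SAP Section 4.
3. State time zero for patients already on DE or VKA for a previous VTE.
4. Report by arm the days from diagnosis to initiation and from initiation to consent, and list events before first intake.
5. Add two sensitivity Cox runs: delayed entry at consent, and the diagnosis clock.

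The cost is wording, one table, one listing and two model runs. Diagnosis and treatment start dates (protocol 9.3.1.1) and the informed consent form (SAP 7) are already among the baseline data.

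There are two downsides. Events before first intake leave the main analysis and appear only in the listing and the diagnosis-clock run. The delayed-entry run has somewhat fewer events and omits early bleeds that the protocol wants kept, so it should remain a sensitivity analysis.

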6.2 IMPORTANT PROTOCOL DEVIATIONS

Patients with important protocol deviations (IPDs) will be documented. The list of all protocol deviations (PDs) and their handling rules are documented in detail in the separate document Protocol Deviation Specification. Additional IPDs may be defined during the course of the study, based on assessments at the MQRMs; if the list of IPDs needs to be enlarged, it will be documented in the report planning meeting minutes before database lock.

